#### (4) Eye Examinations Schedule

As shown in Table 6-1, the examination and observation are carried out for the period from before surgery day 120 to 180 after surgery of second eye. At Visit 0 and Visit 4A, the examination and observation of both eyes are carried out on the same day.

Both the examination and the observation may be per Visited on the same day if the day is within the window for the examination and observation of the eye concerned (first or second operated eye). Also examination and observation can be performed separately over days if these are performed within the set window.

Table 6-1 Eye Examinations Schedule

PROCEDURES/ MEASUREMENTS/ STATUS	Visit 0 (Preop)	Visit 00 (Op)	Visit 00A (Op)	Visit 1 (d1-2)	Visit 1A (d1-2)	Visit 2 (d7-14)	Visit 2A (d7-14)	Visit 3 (d30-60)	Visit 3A (d30-60)	Visit 4A (d120-180)
Informed Consent*	X									
Demographics	X									
Inclusion/Exclusion Criteria	X	1 st	2 nd							
Urine Pregnancy Test (female only)	X									
Intraocular Pressure	B			1 st	2 nd	1 st	2 nd	1 st	2 nd	B
Laser Flare Meter (mydriatic)						1 st	2 nd			(1 st ) (2 nd )
Slit Lamp Examination	B			1 st	2 nd	1 st	2 nd	1 st	2 nd	B
Dilated Fundus Examination	B					1 st	2 nd			B
Fundus visualization						1 st	2 nd			B
IOL Observations				1 st	2 nd	1 st	2 nd	1 st	2 nd	B
Lens decentration and tilt				1 st	2 nd	1 st	2 nd	1 st	2 nd	B
Subjective Posterior Capsule Opacification / Posterior Capsulotomy					1 st	2 nd	1 st	2 nd	1 st	2 nd
Subjective Symptoms	X b								X b	X b
Operation Records**			1 st	2 nd						
Ocular Concomitant Medications	B	1 st	2 nd	1 st	2 nd	1 st	2 nd	1 st	2 nd	B
Secondary Surgical Interventions				1 st	2 nd	1 st	2 nd	1 st	2 nd	B
Device Deficiencies	↔									
Adverse Events	↔									

1st: First eye, 2nd: Second eye, B: Both eyes (1st eye and 2nd eye), Xb: Binocular Testing, X: Conduct[REDACTED], (1st) (2nd): If there is any inflammation sign at Visit 2 or Visit 2A, perform examination again.

\*: Consent continuously participate of this clinical study is obtained between 1st and 2nd implant.

\*\*: Operative Eye, Problems During Surgery, Other Procedures at Surgery, Insertion Instrument, Incision Site, Final Incision Size, anterior capsulotomy size, and Lens Information

## (5) Examinations Procedure

Below examination and observation are carried out at Visit 0, Visit 00/00A, Visit 1/1A, Visit 2/2A, Visit 3/3A and Visit 4A. The same instruments and methods should be used for all measurements at all visits in each site.

### 1) Preoperative Examination (Visit 0)

- Informed consent

Routine test conducted for cataract subjects is performed. Subjects still qualifies after these tests are explained this study. Ensure that the subject has read, understood, and signed and dated a statement of informed consent prior to undergoing any study specific testing. Even though routine test was operated before informed consent, these data can be use as study data.

- Demography

Sex, age, systemic complication, ophthalmologic surgical history

- Urine Pregnancy Test (female subjects only)

Perform a urine pregnancy test if the subject is female and of childbearing potential.

- Visual acuity

Measure the monocular visual acuity about both eyes. Measure the visual acuity [REDACTED]

[REDACTED] using the 100% contrast chart at each measurement distance as below.

[REDACTED]

[figure not shown]
[REDACTED]

[REDACTED]

[REDACTED]

- Subjective Symptoms

[figure not shown]
To the following inquiries by the investigator or co-investigator, the subject will declare the following Subjective symptoms.

- Target Residual Refractive Error

Indicate the amount of postoperative refractive error ( $\pm$ ) anticipated based on the power calculation software used for the lens power that is chosen. [REDACTED]

- Intraocular pressure

Perform tonometry using a contact or a non-contact ocular tonometer.

- Slit Lamp Examination

Record the presence or absence of clinically significant ophthalmologic findings.

- Dilated Fundus Examination

Record the presence or absence of clinically significant ophthalmologic findings.

- Ocular concomitant medications

Indicate the type of concomitant ocular medications used by the subject at the time of the examination.

- Inclusion/exclusion criteria

Ensure that the subject meets inclusion/exclusion criteria and meet all qualifications for participation.

- Adverse Events, Device Deficiencies

Presence/absence of adverse events and device deficiencies are recorded since informed consent.

## 2) Surgery Day (Visit 00/00A)

Record surgical information at Visit 00 (1st eye) and Visit 00A (2nd eye) respectively, Obtain consent in continuation of the study from each subject prior to the surgery on the 2nd eye.

- Operative Eye

Indicate which eye is being implanted.

- Qualification during the surgery.

Assess qualification according to the inclusion/exclusion criteria during the surgery.

- Incision Site

Record the incision site (sclera, at limbus, or cornea).

- Anterior capsulorhexis Diameter

Indicate anterior capsulorhexis diameter (mm) to the nearest 0.1 mm.

- Final Incision Size

Indicate final incision size (mm) to the nearest 0.1 mm.

- Insertion Instrument

Indicate which approved instrument and cartridge was used to fold and insert the IOL through the wound.

- Problems during surgery

Indicate what problems, if any, occurred during surgery. If any exclusion criteria occur, discontinue the subject from the clinical study.

- Other procedures at this surgery

Any other procedures performed at this surgery should be indicated. Since other procedures at this surgery are included in the exclusion criteria, discontinue the subject from the clinical study.

- Ocular concomitant medications

Indicate the type of concomitant ocular medications (e.g. adrenocorticosteroid, chemotherapy, NSAIDs, IOP reducing drug) used during the surgery.

- Lens Information

Provide the IOL information (IOL model, refractive power, serial No.) also in the event of discontinuation of implant. Attach the adhesive label contained in the package of the investigational lens to the CRF and the Study Participants Card.

- Adverse events and Device deficiencies

[figure not shown]
Presence/absence of adverse events and device deficiencies are recorded.

[figure not shown]
[figure not shown]
### 3) Postoperative Examinations

Below examination and observation are carried out at Visit 1/1A, Visit 2/2A, Visit 3/3A and Visit 4A.

- Visual acuity

Visual acuity is tested under photopic [REDACTED] using the 100% contrast chart at each measurement distance as below. [REDACTED]  
[REDACTED]  
[REDACTED]

- **Subjective Symptoms (Visit 3A, Visit 4A: Binocular)**

To the following inquiries by the investigator, the subject will declare the following Subjective symptoms.

- Intraocular Pressure (Visit 1/1A, Visit 2/2A, Visit 3/3A: Monocular (1st or 2nd eye), Visit 4A: Both eyes)

Perform tonometry using a contact or a non-contact ocular tonometer.

- Laser Flare Meter (Visit 2/2A: Monocular (1st or 2nd eye), Visit 4A: Both eyes)

Perform examination using a laser flare meter at mydriatic condition. If there is any inflammation sign at Visit 2 or Visit 2A in laser flare meter and Slit lamp examination, perform examination again at Visit 4A.

- Slit Lamp Examination (non-mydriatic or mydriatic)

(Visit 1/1A, Visit 2/2A, Visit 3/3A: Monocular (1st or 2nd eye), Visit 4A: Both eyes)

Record the presence or absence of clinically significant ophthalmologic findings.

- Dilated Fundus Examination (Visit 2/2A: Monocular (1st or 2nd eye), Visit 4A: Both eyes)

Record the presence or absence of clinically significant ophthalmologic findings.

- Fundus visualization (Visit 2/2A: Monocular (1st or 2nd eye), Visit 4A: Both eyes)

Indicate whether the investigational lens has caused any loss in fundus visualization that would alter a surgeon's ability to administer retinal treatment, as compared to experience with monofocal IOLs.

- IOL observation (Visit 1/1A, Visit 2/2A, Visit 3/3A: Monocular (1st or 2nd eye), Visit 4A: Both eyes)

[figure not shown]
Observe the IOL surface and the inside of the haptic and optic of the investigational lens with a slit-lamp microscope, and record the presence/absence of visible abnormal findings (debris on IOL surface, forceps mark on IOL surface, glistening, formation of membrane on IOL, pigmentation on IOL, etc.). And regarding the observed findings, evaluate the clinical significance. If the problem may negatively affect postoperative visual acuity, etc., handle it as the clinical significant, and if possible, take photos.

- IOL position change (Visit 1/1A, Visit 2/2A, Visit 3/3A: Monocular (1st or 2nd eye), Visit 4A: Both eyes)

Tilt and/or decentration should be reported if greater than 10 degrees or 0.5mm.

- Posterior Capsule Opacification (PCO) (Visit 1/1A, Visit 2/2A, Visit 3/3A: Monocular (1st or 2nd eye), Visit 4A: Both eyes)

Indicate the presence/absence of PCO. If PCO is present, it will be graded as clinically non-significant, clinically significant or clinically significant requiring YAG as follows:

- Posterior capsulotomy (Visit 1/1A, Visit 2/2A, Visit 3/3A: Monocular (1st or 2nd eye), Visit 4A: Both eyes)

Indicate whether a posterior capsulotomy was performed or not. If it was performed, report the date of the procedure and size.

- Ocular concomitant medications (Visit 1/1A, Visit 2/2A, Visit 3/3A Monocular (1st or 2nd eye), Visit 4A: Both eyes)

Indicate the type of concomitant ocular medications used by the subject at the time of the examination.

- Secondary surgical intervention (Visit 1/1A, Visit 2/2A, Visit 3/3A: Monocular (1st or 2nd eye), Visit 4A: Both eyes)

Record the presence/absence of any postoperative surgical procedure that may be caused by the investigational lens. The SSI include iridotomies/ iridectomy for pupillary block, vitrectomy for pupillary block, adjustment of the position of the investigational lens, removal of the investigational lens due to inflammation, exchange of the investigational lens, etc., but not limited to them. Meanwhile, retinal reattachment surgery and posterior capsule resection are not included as SSI.

- Adverse events and Device efficiencies (Visit 1/1A, Visit 2/2A, Visit 3/3A and Visit 4A)

Presence/absence of adverse events and device efficiencies are recorded.

#### 4) Unscheduled Visits Examinations

When a subject makes an unscheduled visit for adverse events etc., inquire about the reason for the visit and retain the record. The investigator will perform examinations/observations those are necessary and retain

the record. If the visit is associated with any ophthalmologic symptom, identify the eye and retain the record.

(6) Anticipated study period

01-Apr-2017 ~ 30-Jun-2018

## 7. CONCOMITANT THERAPY

(1) Permissible concomitant therapy

The use of spectacles and contact lenses is permitted.

(2) Prohibited concomitant therapy

Concomitant application of other ways of correcting refraction, possibly affecting evaluation of the investigational lens, is prohibited during the study. For example, laser in situ keratomileusis, PRK and refraction corrective contact lens (orthokeratology).

## 8. DISCONTINUED SUBJECTS

(1) Discontinued Subjects

The subject is discontinued in the following cases:

- 1) The investigational lens was removed for reasons of adverse events.
- 2) The investigator (or sub-investigator) judged it necessary to replace the investigational lens with another IOL.
- 3) The investigator (or sub-investigator) judged it necessary to discontinue the subject from the study.
- 4) The subject canceled the consent once issued.
- 5) The subject requested discontinuation of the study.
- 6) Continuation of the study was judged as impossible because of subject's referral or move during the study.
- 7) Other (discontinuation is necessary)

Upon discontinuation of the study, if the investigator or sub-investigator decided the examination or observation is necessary, the examination or observation should be carried out as far as possible under the subject's consent, and the date and reason of discontinuation are entered in the electric case report form. In case where continuation of the study is difficult because of discontinued visit of the subject to the clinic, the subject is followed over telephone, by mail or other appropriate means and the reason for discontinued visit, survival/death of the subject, presence/absence of adverse events, etc., are entered in the electric case report form.

If the investigational lens remained implanted in the subject after discontinuation of the study, the subject is informed as to the necessity of receiving periodical ophthalmological follow-up to assure safety at least 6 months after surgery, and the subject is asked to extent cooperation as much as possible.

## (2) Discontinuation of the entire study

If discontinuation of the entire study has become inevitable for reasons of reports on serious safety information from any participating study site or overseas, problems pertaining to the quality of the investigational lens, and so on, the Sponsor is required to immediately inform the investigator and the head of each study site of discontinuation of the study and its reason in writing.

# 9. Analysis Plan

## 9.1 Subject Evaluability

The final subject evaluability will be determined prior to database lock. Analysis datasets used for safety and effectiveness analyses of this study are defined as follows.

### 9.1.1 Safety Analysis Set

The pre-treatment safety analysis set will include all subjects who consented to participate in the study.

The pre-treatment safety analysis set will be the set that will be used to summarize occurrence of adverse experiences prior to exposure to the test article. The treatment-emergent safety analysis set will include all eyes with attempted implantation with the test article (successful or aborted after contact with the eye).

### 9.1.2 All-Implanted Analysis Set (AAS)

All-Implanted Analysis Set (AAS) will include all eyes with successful test article implantation.

### 9.1.3 Best-Case Analysis Set (BAS)

Best-Case Analysis Set (BAS) will include all eyes with successful test article implantation that had

[figure not shown]
- at least 1 postoperative visit;
- no macular degeneration at any time; and
- no major protocol violation

## 9.2 Analysis Dataset

Analysis datasets used for effectiveness and safety analyses are as follows.

### 9.2.1 Dataset for Primary Effective Analysis

AAS and BAS will be used for primary effectiveness analysis. The primary analysis set for effectiveness analyses will be the AAS.

### 9.2.3 Dataset for Safety Analysis

Pre-treatment safety analysis set will be used for adverse experiences prior to exposure to the test article. The treatment-emergent safety analysis set will be used for all safety variables after contact with the test article.

## 9.3 Demographics and Baseline Characteristics

For all analysis datasets (Safety Analysis Set, AAS and BAS), demographics (sex, age [ $<60$ ,  $60-69$ ,  $70-79$ ,  $\geq 80$ ], systemic complication [None/Yes, details] and past ocular surgery [None/Yes, details]) will be summarized with the number and percent of subjects in each category for the variable. Age will also be summarized with descriptive statistics (mean, standard deviation, number of subjects, median, min and max).

## 9.4 Effectiveness Analysis

The objective of this study is to describe safety and effectiveness of the investigational lens (TFNT00) when implanted to replace the natural lens following cataract removal. Monocular analysis will be performed at both first and second eyes. Binocular analysis will be performed for binocular testing parameters.

### 9.4.1 Primary Analysis

Primary effectiveness variables are as follows.

- Monocular photopic best corrected distance visual acuity (5 m)
- Monocular photopic distance corrected intermediate visual acuity (60 cm)
- Monocular photopic distance corrected near visual acuity (40 cm)

#### 9.4.1.1 Statistical Hypothesis

No formal hypothesis testing is planned.

#### 9.4.1.2 Analysis Method

Decimal monocular photopic best corrected distance visual acuity (5 m) and decimal monocular photopic distance corrected intermediate visual acuity (60 cm) will be categorized as follows.

[figure not shown]
- $< 0.5$
- $0.5 - < 0.7$
- $0.7 - < 1.0$
- $1.0 -$

[figure not shown]
Decimal monocular photopic distance corrected near visual acuity (40 cm) will be categorized as follows.

- $< 0.4$
- $0.4 -$

The N and percent of each category will be provided by visit. For these decimal visual acuity, descriptive statistics (geometric mean, dispersion factor (DF), N, median, min and max) will be provided by visit. Descriptive statistics (arithmetic mean, standard deviation, N, median, min and

max) will also be provided for logMAR visual acuity by visit.

## 9.5 Handling of Missing Data

No missing data will be imputed.

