2.1 Efficacy Analysis Sets

All Implanted Analysis Set (AAS):

All-Implanted Analysis Set (AAS) will include all eyes with successful test article implantation.

Best Case Analysis Set (BAS):

Best-Case Analysis Set (BAS) will include all eyes with successful test article implantation that had

- at least 1 postoperative visit;
- no macular degeneration at any time; and
- no major protocol violation

AAS and BAS will be used for primary effectiveness analysis. The primary analysis set for primary effectiveness analyses will be the AAS. [REDACTED]

[REDACTED]

[REDACTED]

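### Do the Visit 4A acuity percentages need a stated denominator and a rule for eyes whose lens was removed or replaced?

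*Protocol*

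**What the plan says.** The primary effectiveness set is defined in SAP 2.1 (and Protocol 9.1.2 and 9.2.1): "All-Implanted Analysis Set (AAS) will include all eyes with successful test article implantation". No postoperative visit is required for membership.

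The three primary variables are corrected acuities at 5 m, 60 cm and 40 cm. Protocol 9.4 says "Monocular analysis will be performed at both first and second eyes", and Protocol 9.4.1.2 says "The N and percent of each category will be provided by visit". SAP 4.3 repeats the second statement. N also appears among the by-visit descriptive statistics. Neither section says what the percent is a percent of.

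On missing values, Protocol 9.5 has one sentence: "No missing data will be imputed".

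Protocol 8(1) discontinues the subject, not only the eye, when "The investigational lens was removed for reasons of adverse events" or when the investigator "judged it necessary to replace the investigational lens with another IOL". A further examination at that point takes place "if the investigator or sub-investigator decided the examination or observation is necessary". In every case "the date and reason of discontinuation are entered in the electric case report form".

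**The concern.** Put together, these passages suggest a mismatch between label and content. The primary set is named for all implanted eyes, but an eye whose lens was taken out would have no Visit 4A acuity, would not be imputed, and so would vanish from the Visit 4A percentages along with its fellow eye. Earlier visits are unaffected. If lenses come out because they disappointed, the remaining eyes are a favourable selection.

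The visible SAP adds to the impression. It plans listings of eyes with missing follow-up values for fundus visualization, intraocular pressure, slit lamp and dilated fundus examination (SAP 5.3.4 to 5.3.7), but shows none for the three primary acuity variables. In a single-arm study without tests, the by-visit percentages are the effectiveness result, so an unstated denominator deserves a look.

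**Working it through.** **1. The plan's own precision figures.** Protocol 9.8 and SAP 8 give, for n = 60, a half-width of 0.26 SD and an exact 95% interval of 36.8% to 63.2% for 30/60. Check: t(0.975; 59)/√60 = 2.001/7.746 = 0.258 SD, and the Clopper-Pearson interval for 30/60 is 36.81% to 63.19%. Both reproduce. They treat 60 eyes (one eye order) as the unit, which is the unit used below.

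**2. What the denominator does.** Let k of 60 eyes of one eye order have no Visit 4A acuity, and let s of the 60 − k measured eyes reach the threshold (that is, fall outside the lowest category: 0.5 or better at 5 m and 60 cm, 0.4 or better at 40 cm).

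- Eyes measured: s/(60 − k)
- All implanted, lost eyes counted as not reaching: s/60
- All implanted, lost eyes counted as reaching: (s + k)/60

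The documents give no removal, replacement or loss rate, so every k is an assumption.

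If all measured eyes reach, the table shows 100%. Counting the lost eyes as not reaching gives:

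| k | s/60 | Exact 95% interval |
|---|---|---|
| 1 | 59/60 = 98.3% | 91.1 to 100.0% |
| 2 | 58/60 = 96.7% | 88.5 to 99.6% |
| 3 | 57/60 = 95.0% | 86.1 to 99.0% |
| 6 | 54/60 = 90.0% | 79.5 to 96.2% |

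If 6 measured eyes miss the threshold, the figures run in both directions:

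| k | Reported | None of the lost reach | All of the lost reach |
|---|---|---|---|
| 1 | 53/59 = 89.8% | 88.3% | 90.0% |
| 3 | 51/57 = 89.5% | 85.0% | 90.0% |
| 6 | 48/54 = 88.9% | 80.0% | 90.0% |

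A mixed case for k = 3: one eye lost its own lens and is counted as not reaching, and two are good fellow eyes lost with their subjects. Then (51 + 2)/60 = 88.3% against 89.5% reported, a gap of 1.1 points before rounding. The exact interval for the reported 51/57 is 78.5% to 96.0%, about 17 points wide.

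**3. Whether the direction is known.** It is not. The endpoints are corrected acuities, a lens can be removed for a reason that leaves corrected acuity good, and half of the eyes lost this way are fellow eyes with nothing wrong.

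**4. Whether the lost eyes can be found.** They can, in the visible text.

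- Removal for inflammation and lens exchange are named as secondary surgical interventions (Protocol 6(5), postoperative examinations; Appendix A), and such interventions are also adverse events (Protocol 10(1)).
- SAP 5.3.1 gives a subject listing, with visit and split by eye order, for interventions related to the optical properties. SAP 5.3.2 covers the others and displays all adverse event information by subject.
- Protocol Table 6-1 schedules intraocular pressure, slit lamp, dilated fundus and fundus visualization for both eyes at Visit 4A. An eye absent at Visit 4A, fellow eyes included, therefore falls under the four missing-value listings in SAP 5.3.4 to 5.3.7, sorted by eye order, subject and visit. These run on the treatment-emergent safety set, which covers attempted implantations (SAP 2.2) and so contains every eye in the primary set.
- SAP 3 plans a subject disposition table.

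**5. What cannot be checked.** The SAP contents list places section 4.3 from page 9 and section 4.4 on page 13, and three blanked table titles all fall on page 12. SAP 2.1 also has blacked-out lines just after naming the primary set. A denominator rule or an acuity listing could sit there, so its absence from the visible text is not evidence that the plan lacks it.

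**The case for a change.** The best case for a change is this. Percent by visit can be programmed over measured eyes or over all implanted eyes, and both fit the text. Comparing the all-implanted with the best-case set does not expose the loss, because an eye without a Visit 4A value is absent from both tables. The safety listings are an imperfect substitute: the intervention listing does not cover fellow eyes, replacement need only be judged necessary for discontinuation to follow, and the missing-value listings do not name the reason for loss. The reason is already on the case report form, so reason rows and an acuity listing would cost little.

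Part of this stands. The denominator is not written, no visible listing is specific to missing acuity, and a reader must combine several outputs to learn why N falls at Visit 4A.

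The rest carries less weight. With imputation ruled out and N reported at each visit, measured eyes is the reading an analyst would adopt, and N makes it visible on the page. Fellow eyes missed by the intervention listing fall under the missing-value listings. Counting a removed lens as not reaching is a different matter from clarification: it replaces a summary of measured acuity with a composite outcome, assigns a category that was not observed, and needs an exception to Protocol 9.5. That is a debatable choice of what to estimate, not the repair of an error.

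**Conclusion.** No change to the plan follows. The unstated denominator is a gap in detail that analysts would fill sensibly, as eyes with data at that visit, and a table footnote would record it. A by-visit summary of measured eyes, with N shown and the losses traceable elsewhere, is sound for a study that SAP 1.1 calls descriptive and that has no hypothesis (Protocol 9.4.1.1, SAP 4.2) and no success criterion (SAP executive summary).

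On size: each lost eye moves a Visit 4A percentage by about 1.5 to 1.7 points if it is counted as not reaching. With 3 of 60 lost and 51/57 reported, the report would be at most 4.5 points too high or 0.5 points too low, and 1.1 points too high in the mixed case. With 6 lost and 48/54 reported, it could be 8.9 points too high or 1.1 too low, but that high-side figure needs 10% of one eye order to be lost and every lost eye to fail. No stated figure or decision changes in any of these cases.

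The conclusion rests on assumed values of k, on the measured-eyes reading, and on the visible text of a SAP section that is partly blacked out. If many subjects were discontinued for lens removal or replacement, the Visit 4A percentages should be read beside the disposition table and the intervention listing.
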